#### 18.2.1. Laboratory Specific Derivations

All datapoints obtained after informed consent up to 60 days after IMP discontinuation or database cutoff will be considered.

- The following abnormality categories will be defined:
  - Low: value < lower limit of normal range

  - $\hspace{0.5cm} \circ \hspace{0.5cm} \text{Normal: lower limit of normal range} \leq \text{value} \leq \text{upper limit of normal range} \\$
  - o High: value > upper limit of normal range

Document:

Author:

Version Number:

V2.0

Version Date:

31JAN2024

Template No.: CS TP BS016 Revision 7 Reference: CS WI BS005

Effective Date: 01Nov2021

Statistical Analysis Plan

Page 68 of 78

- Notes:
  - Classification will be done in standardized units, using non imputed values and limits.
  - For the worst-case analysis visits, as defined in Section 6.4, an additional category low + high is defined in case there are both low and high post-baseline values.

Toxicity grades will be computed according to the National Cancer Institute (NCI) common toxicity criteria for adverse events (CTCAE) toxicity grading list (version 5.0). The implementation of these toxicity grades for analysis is presented in appendix 2. Only the parameters described in appendix 2 will be computed, according to the declared limits for each grade.

Only lab parameters specified within the protocol will be analysed and, only those both in the protocol and in appendix 2 will be considered for toxicity. All others that are in the protocol and not in appendix 2, but have High/Low/Normal will be presented in the abnormality table.

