# **10.2.** Appendix 2: Clinical Laboratory Tests

The tests listed in Table 6 will be performed as described in the laboratory manual.

Protocol-specific requirements for the inclusion and exclusion of participants are detailed in Section 5.1 and Section 5.2, respectively.

Additional tests may be performed during the study as determined necessary by the investigator or required by local regulations.

Investigators must document their review of each laboratory test result.

**Table 6:** Protocol-Required Safety Laboratory Tests

Laboratory test	Parameters		
Hematology	RBC count platelet count hemoglobin hematocrit	RBC indices: MCV MCH	WBC count with differential: neutrophils eosinophils lymphocytes basophils monocytes
Serum chemistry	ALT AST albumin a BUN bilirubin (total and direct) creatinine	GFR glucose potassium sodium calcium chloride bicarbonate	total protein a creatine kinase HbA1C HDL LDL triglycerides C-reactive protein
Routine urinalysis	
 
Specific gravity
 
pH, glucose, protein, blood, ketones, bilirubin, urobilinogen, nitrite, leukocyte esterase
 
Microscopic examination (if blood or protein is abnormal)
 
Urine protein quantitative analysis (if protein is abnormal)
 
		
Pregnancy testing	Highly sensitive serum hCG pregnancy serum test at screening and urine test at other time points (as needed for WOCBP potential, defined in Section 10.4.1)		
Other tests	
 
SARS-CoV-2 nasopharyngeal swab test (PCR) (if applicable)
 
HBV, HCV, HIV (refer to exclusion criterion 4 and Sections 10.2.1.2, 10.2.1.3, and 10.2.1.4, respectively)
 
Menopausal test (FSH) if applicable (to confirm non-WOCBP status)
 
IgGa (to verify exclusion criterion 11)
 
		

<sup>a This result will be blinded postbaseline.

ALT=alanine aminotransferase; AST=aspartate aminotransferase; BUN=blood urea nitrogen; FSH=follicle-stimulating hormone; GFR=glomerular filtration rate; HbA1C=glycated hemoglobin; HBV=hepatitis B virus; hCG=human chorionic gonadotropin; HCV=hepatitis C virus; HDL=high-density lipoprotein; IgG=immunoglobulin G; LDL=low-density lipoprotein; MCH=mean corpuscular hemoglobin; MCV=mean corpuscular volume; PCR=polymerase chain reaction; RBC=red blood cell; WBC=white blood cell; WOCBP=women of childbearing potential

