## 6.5. Treatment-emergent Abnormality/Toxicity

A treatment-emergent abnormality/toxicity (for laboratory assessments, vital signs, or ECGs) is defined as any postbaseline abnormality/toxicity that was not present at baseline (e.g. hemoglobin normal at baseline and grade 1 postbaseline; glucose low at baseline and high postbaseline; QTcF [450; 480] ms at baseline and >500 ms postbaseline).

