#### **Laboratory Assessments**

Hematology	RBC count, platelet count, hemoglobin, hematocrit, MCV, MCH, WBC count with differential: neutrophils, eosinophils, lymphocytes, basophils, monocytes
Serum chemistry	ALT, AST, albumin, blood urea nitrogen, creatinine, eGFR, glucose, potassium, chloride, bicarbonate, sodium, total protein, calcium, bilirubin (total and direct) creatine kinase, HbA1C, HDL, LDL, triglycerides, C-reactive protein
Routine urinalysis	Specific gravity, pH, glucose, protein, blood, ketones, bilirubin, urobilinogen, nitrite, leukocyte esterase, microscopic examination (if blood or protein is abnormal)  Urine protein quantitative analysis (if protein is abnormal)
Pregnancy testing	Highly sensitive serum hCG pregnancy serum test at screening and urine test at other time points (as needed for WOCBP potential,)
Other tests	SARS-CoV-2 nasopharyngeal swab test (PCR) (if applicable)  HBV, HCV, HIV  Menopausal test (FSH) if applicable (to confirm non-WOCBP status)  IgG a

a This result will be blinded postbaseline.

 $ALT= a lanine\ aminotransferase;\ AST= a spartate\ aminotransferase;\ BUN= blood\ urea\ nitrogen;\ FSH= follicle-stimulating\ hormone;$ 

Document:

Author:

Version Number:

V2.0

Version Date:

31JAN2024

Template No.: CS\_TP\_BS016 Revision 7 Reference: CS\_WI\_BS005

Effective Date: 01Nov2021

Statistical Analysis Plan

Page 67 of 78

GFR=glomerular filtration rate; HbA1C=glycated hemoglobin; HBV=hepatitis B virus; hCG=human chorionic gonadotropin; HCV=hepatitis C virus; HDL=high-density lipoprotein; IgG=immunoglobulin G; LDL=low-density lipoprotein; MCH=mean corpuscular hemoglobin; MCV=mean corpuscular volume; PCR=polymerase chain reaction; RBC=red blood cell; WBC=white blood cell; WOCBP=women of childbearing potential

Normal ranges are available as provided by the central laboratory and results will be presented in standardized units unless specified otherwise. Clinically significant changes occurring during the study are recorded as an AE.

Quantitative laboratory measurements reported as "< X", i.e. BLQ, or "> X", i.e. above the upper limit of quantification (ULQ), will be converted to X for the purpose of quantitative summaries, but will be presented as recorded, i.e. as "< X" or "> X" in the listings.

Continuous laboratory parameters will be summarized using descriptive statistics of actual values and changes from baseline at each analysis visit. Categorical parameters will only be listed.

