#### **APPENDIX 2.** TOXICITY GRADES

The table below shows how the CTCAE, v5.0: 27 Nov 2017 will be implemented in the analysis.

Parameter	Unit	Grade 1	Grade 2	Grade 3	Grade 4
Alanine amino transferase		>1-3 *ULN	>3-5 *ULN	>5-20 *ULN	>20 *ULN
Albumin	g/L	<lln-30< td=""><30-20	<20	-	</lln-30<>	<30-20	<20	-
	g/dL	<lln-3< td=""><3-2	<2	-	</lln-3<>	<3-2	<2	-
Alkaline phosphatase		>1.0-2.5 *ULN	>2.5-5.0 *ULN	>5.0-20.0 *ULN	>20.0 *ULN
Aspartate amino transferase		>1-3 *ULN	>3-5 *ULN	>5-20 *ULN	>20 *ULN
Bilirubin (total)		>1.0-1.5 *ULN	>1.5-3.0 *ULN	>3.0-10.0 *ULN	>10.0 *ULN
Calcium (ionized) low	mmol/L	<lln-1.0< td=""><1.0-0.9	<0.9-0.8	<0.8	</lln-1.0<>	<1.0-0.9	<0.9-0.8	<0.8
	mg/dL	<lln-4.0< td=""><4.0-3.6	<3.6-3.2	<3.2	</lln-4.0<>	<4.0-3.6	<3.6-3.2	<3.2
Calcium (ionized)	mmol/L	>ULN-1.5	>1.5-1.6	>1.6-1.8	>1.8
high	mg/dL	>ULN-6.0	>6.0-6.4	>6.4-7.2	>7.2
Calcium (corrected)	mmol/L	<lln-2.00< td=""><2.00-1.75	<1.75-1.50	<1.50	</lln-2.00<>	<2.00-1.75	<1.75-1.50	<1.50
low	mg/dL	<lln-8< td=""><8-7	<7-6	<6	</lln-8<>	<8-7	<7-6	<6
Calcium (corrected)	mmol/L	>ULN-2.9	>2.9-3.1	>3.1-3.4	>3.4
high	mg/dL	>ULN-11.5	>11.5-12.5	>12.5-13.5	>13.5
Cholesterol	mmol/L	>ULN-7.75	>7.75-10.34	>10.34-12.92	>12.92
	mg/dL	>ULN-300	>300-400	>400-500	>500
Creatine kinase		>1.0-2.5 *ULN	>2.5-5.0 *ULN	>5.0-10.0 *ULN	>10.0 *ULN
Creatinine		>1.0-1.5 *ULN	>1.5-3.0 *ULN	>3.0-6.0 *ULN	>6.0 *ULN
Glucose (fasting) low	mmol/L	<lln-3.0< td=""><3.0-2.2	<2.2-1.7	<1.7	</lln-3.0<>	<3.0-2.2	<2.2-1.7	<1.7
	mg/dL	<lln-55< td=""><55-40	<40-30	<30	</lln-55<>	<55-40	<40-30	<30
Lipase		>1.0-1.5 *ULN	>1.5-2.0 *ULN	>2.0-5.0 *ULN	>5.0 *ULN
Potassium low	mmol/L	-	<lln-3.0< td=""><3.0-2.5	<2.5	</lln-3.0<>	<3.0-2.5	<2.5
	mEq/L	-	<lln-3.0< td=""><3.0-2.5	<2.5	</lln-3.0<>	<3.0-2.5	<2.5
Potassium high	mmol/L	>ULN-5.5	>5.5-6.0	>6.0-7.0	>7.0

Document:

Author:

Version Number:

V2.0

Version Date:

31JAN2024

Template No.: CS\_TP\_BS016 Revision 7

Reference: CS\_WI\_BS005

Effective Date: 01Nov2021

Statistical Analysis Plan

Page 76 of 78

Parameter	Unit	Grade 1	Grade 2	Grade 3	Grade 4
	mEq/L	>ULN-5.5	>5.5-6.0	>6.0-7.0	>7.0

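### SAP 6.5 uses a hemoglobin grade as its example, but Appendix 2 has no hemoglobin row, so worsening from a low baseline is not counted in the categorical laboratory tables

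*SAP*

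**What the plan says.** Hemoglobin is among the required hematology tests in protocol Section 10.2, Table 6 ("RBC count platelet count hemoglobin hematocrit"). The SAP repeats it in its own list under Section 18.2 ("RBC count, platelet count, hemoglobin, hematocrit, MCV, MCH, WBC count with differential").

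SAP 6.5 defines a treatment-emergent finding as "any postbaseline abnormality/toxicity that was not present at baseline (e.g. hemoglobin normal at baseline and grade 1 postbaseline", followed by a glucose example and a QTcF example. The first illustration is thus a hemoglobin grade.

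SAP 18.2.1 limits grading: "Only the parameters described in appendix 2 will be computed, according to the declared limits for each grade", and "only those both in the protocol and in appendix 2 will be considered for toxicity". For the rest it gives a fallback: "All others that are in the protocol and not in appendix 2, but have High/Low/Normal will be presented in the abnormality table". In that classification, low means any value under the lower limit of normal, with no further subdivision.

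Appendix 2 opens with "The table below shows how the CTCAE, v5.0: 27 Nov 2017 will be implemented in the analysis". Its blood-count rows are CD4 count, lymphocytes, neutrophils, platelets and white blood cells. There is no hemoglobin row, and the published table shows no gap or blacked-out text where one would stand.

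SAP 18.2 plans a shift table against baseline for toxicity grades. For low/normal/high abnormalities it plans both a shift table and a count of participants with treatment-emergent abnormalities.

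**The concern.** Section 6.5 presupposes a hemoglobin grade, and Section 18.2.1 with Appendix 2 rules one out. A programmer who follows 18.2.1 cannot produce the output that 6.5 describes.

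The practical loss concerns participants who enter with low hemoglobin. With only three categories, and with treatment-emergent defined as not present at baseline, further worsening leaves the category unchanged. That is less than 6.5 appears to intend: its QTcF example counts a move from one abnormal band to a worse one as treatment-emergent. Platelets, neutrophils, lymphocytes and white cells can show such worsening in the grade shift table. Hemoglobin cannot.

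At stake is part of the laboratory component of the secondary safety objective. In a trial of about 30 participants, shifts in single individuals are informative.

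**Working it through.** The plan states no figure on this point, so there is nothing to reproduce. The check compares the passages and applies the stated rule.

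**Step 1: which hematology tests are graded.** Protocol Table 6 and SAP 18.2 list 12 parameters: RBC, platelets, hemoglobin, hematocrit, MCV, MCH, WBC, neutrophils, eosinophils, lymphocytes, basophils and monocytes. Appendix 2 has rows for 4 of them: platelets, WBC, neutrophils and lymphocytes. The other 12 − 4 = 8, hemoglobin included, go to low/normal/high only.

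**Step 2: apply 6.5 to three categories.** The documents give no normal range for hemoglobin. For illustration, assume 120 to 160 g/L.

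| Baseline (g/L) | Postbaseline (g/L) | Categories | Treatment-emergent? |
|---|---|---|---|
| 130 | 115 | Normal to Low | Yes |
| 118 | 75 | Low to Low | No |
| 115 | 95 | Low to Low | No |
| 118 | 165 | Low to High | Yes |

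The result does not depend on the assumed range. Let L be any lower limit, b the baseline value and p the later value. If b < L and p < b, then p < L, so the category stays Low and nothing is counted.

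**Step 3: the worst-case visit.** SAP 18.2.1 adds only a combined low-and-high category there. A participant who is low throughout is still low to low.

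**Step 4: where the fall would still be seen.** SAP 18.2 summarizes hemoglobin values and their change from baseline by visit, and SAP 7.2 includes minimum, quartiles and maximum in safety descriptive statistics. Take the 118 to 75 case, a change of 75 − 118 = −43 g/L, in an arm of 20 (the efgartigimod number in protocol Section 9.5). The arm mean moves by only 43/20 = 2.15 g/L, but the minimum at that visit would be 75 g/L or lower and the largest fall at least 43 g/L. SAP 18.2 also lists participants who have abnormal values after baseline.

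**Step 5: would a new row be enough?** Not by itself. SAP 18.2 states a treatment-emergent count for abnormalities but not for grades, so a new row would yield a grade shift table and no count. Read literally, the fallback in 18.2.1 sends only parameters outside Appendix 2 to the abnormality table. Adding hemoglobin to Appendix 2 could therefore remove it from the one table that has a stated treatment-emergent count.

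**The case against.** The strongest reply is that little is lost.

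- **Laboratory outputs.** The protocol endpoint is change in laboratory safety evaluations, and change is reported. The minimum value and the largest fall are tabulated by visit, and abnormal cases are listed. With about 30 participants they can be read one by one.
- **Adverse events.** Clinically significant laboratory changes are recorded as adverse events, including worsening of pre-existing conditions (protocol Sections 8.3, 8.3.4 and 10.3.1). They are graded by CTCAE v5.0 (protocol Section 10.3.3). SAP 18.1 and 18.1.1 tabulate events of grade 3 or above, and events by worst toxicity, by arm.
- **The example.** In 6.5 it is only an illustration. A normal-to-low change is still counted as treatment-emergent; only the grade label is lost.

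Most of this stands. A reader might infer that the plan cannot show the severity of anaemia by arm. The documents do not support that, given the outputs just listed.

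What remains is narrower. Descriptive statistics are group summaries, and a listing gives no count by arm and severity. The adverse event route depends on judgment: protocol Sections 8.3.4 and 10.3.1 exempt laboratory findings tied to the underlying disease unless they are more severe than expected, and protocol Section 8.2.3 includes a hematological domain in the ESSDAI. Some worsening may therefore never become an adverse event.

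**Conclusion.** The point holds as an internal inconsistency with a limited reporting consequence. SAP 6.5 and Appendix 2 do not agree on hemoglobin. In the categorical laboratory tables, a further fall from a low baseline produces no shift and no treatment-emergent count. This follows from the SAP text for any normal range. It assumes that the published Appendix 2 is complete, and nothing in it suggests otherwise.

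The size is small. One required parameter is affected, in one type of table, and other outputs partly cover it. No number of affected participants can be given, because the documents do not report how common low hemoglobin is at baseline. Any assumed share would give only a ceiling on those who could worsen unseen in these tables.

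A reader might also infer that the Appendix 2 rows for tests absent from Table 6, such as alkaline phosphatase, cholesterol and lipase, distort the analysis. They do not, because 18.2.1 already limits grading to parameters that are also in the protocol.

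**What to change.** Make three changes together:

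1. Add a hemoglobin (low) row to Appendix 2, with limits taken from the CTCAE v5.0 list that the SAP already adopts.
2. State in SAP 18.2 that the number of participants with a treatment-emergent toxicity, meaning a grade not present at baseline as in 6.5, will be shown by arm.
3. State that hemoglobin also stays in the low/normal/high abnormality table.

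The second and third are needed because the row alone would add a shift table without a count and could take hemoglobin out of the abnormality table.

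If hemoglobin was left ungraded on purpose, the SAP should say so, replace the example in 6.5 and state how worsening from a low baseline will be reported.

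The cost is one table row, one or two sentences and standard programming. No new data are needed.

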#### 18.3. ECG Evaluations

Results from the central ECG (Electrocardiogram) Reading Centre will be included in the reporting of this study. Single 12-lead ECG(s) will be obtained using an ECG machine. The following ECG parameters will be reported for this study:

- HR (bpm)
- PR Interval (msec)
- QRS Interval (msec)
- RR Interval (msec)
- QT Interval (msec)
- QTcF Interval (msec)
- QTcB Interval (msec)

All datapoints obtained after informed consent up to 60 days after IMP discontinuation or database cutoff will be considered.

The following summaries will be provided for ECG data:

- ECG parameters will be summarized using descriptive statistics at each analysis visit.
- Abnormalities of the actual values will be presented as cross-tabulations of the abnormality at each postbaseline
  analysis visit and at the worst-case analysis visit versus the baseline abnormality. Numbers and cumulative

Document:

Author:

Version Number: V2.0

Version Date: 31JAN2024

Template No.: CS TP BS016 Revision 7 Reference: CS WI BS005

Effective Date: 01Nov2021

Statistical Analysis Plan

Page 69 of 78

numbers (QTc only) of participants with treatment-emergent abnormalities will also be shown. The denominator for the percentage is the total number of participants per treatment arm and per analysis visit.

- Abnormalities of the QTc changes will be presented as tabulations of the change abnormality at each
  postbaseline analysis visit and at the worst-case analysis visit. Cumulative numbers of participants with change
  abnormalities will also be shown. The denominator for the percentage is the total number of participants per
  treatment arm and per analysis visit.
- All ECG data will be listed, but only for participants with any postbaseline abnormality.

#### 18.3.1. ECG Abnormal Criteria

Abnormal quantitative ECG measurements will be identified in accordance with the following predefined abnormal criteria for HR, QRS and PR interval:

	HR (bpm)	PR (ms)	QRS (ms)
Low	<40	<120	-
Normal	40-100	120-220	0-120
High	>100	>220	>120

Note: For the worst-case analysis visit, as defined in Section 6.4, an additional category "low + high" is defined if there are both low and high postbaseline values.

Actual values for QT interval, QTcB interval and QTcF will be classified as:

- Actual values:
  - $\circ \le 450 \text{ (normal)}$
  - o ]450; 480]
  - 0 ]480; 500]
  - > 500
- Changes from baseline:
  - $\circ \le 30 \text{ (normal)}$
  - 0 ]30; 60]
  - o > 60

Note: The worst-case, as defined in Section 6.4, is the highest postbaseline value and associated change.

Document:

Author:

Version Number: V2.0

Version Date: 31JAN2024

Template No.: CS TP BS016 Revision 7 Reference: CS WI BS005

Effective Date: 01Nov2021

Statistical Analysis Plan

Page 70 of 78

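### SAP 18.3.1 puts uncorrected QT under the same interval classes as QTcB and QTcF, and disagrees with SAP 18.3 on whether QT changes are tabulated

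*SAP*

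**What the plan says.** SAP 18.3 lists uncorrected QT as a reported ECG parameter beside QTcF and QTcB. SAP 18.3.1 then sets the criteria under one lead-in, "Actual values for QT interval, QTcB interval and QTcF will be classified as". The actual-value classes are up to 450 ms (normal), above 450 to 480, above 480 to 500, and above 500. Below them, under "Changes from baseline", come up to 30 ms (normal), above 30 to 60, and above 60. No separate limits are given for uncorrected QT. A note adds: "The worst-case, as defined in Section 6.4, is the highest postbaseline value and associated change".

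SAP 18.3 says how these classes are used:

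- Actual values: "Abnormalities of the actual values will be presented as cross-tabulations of the abnormality at each postbaseline" visit and at the worst-case visit, against baseline. This is not limited to QTc.
- Counts: numbers and cumulative "numbers (QTc only) of participants with treatment-emergent abnormalities will also be shown".
- Changes: "Abnormalities of the QTc changes will be presented as tabulations of the change abnormality at each" visit and at the worst case. Only QTc is named.
- Listing: ECG data are listed for participants with any postbaseline abnormality.

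SAP 6.5 supplies the definition: "A treatment-emergent abnormality/toxicity (for laboratory assessments, vital signs, or ECGs) is defined as any postbaseline abnormality/toxicity that was not present at baseline". Its ECG example uses QTcF.

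**The concern.** Uncorrected QT varies with heart rate. Fixed limits that are workable for a rate-corrected interval therefore sort uncorrected QT partly by heart rate. A slow rate can push QT above 450 ms while QTcF is normal, and a fast rate can leave QT below 450 ms while QTcF is prolonged. The worst-case rule takes the highest postbaseline value, which for uncorrected QT favours the ECG recorded at the slowest rate.

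There is also a plain mismatch. SAP 18.3.1 defines change classes under a lead-in that names QT, while 18.3 plans change tables for QTc only. A programmer cannot tell whether a QT change table is wanted.

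ECG change is part of a secondary safety endpoint (Protocol Section 3, Table 1). About 30 participants are randomized 2:1, so roughly 10 are on placebo and one heart-rate-driven flag in that arm would read as 10%.

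**Working it through.** The plan states no figure on this point, so there is none to reproduce.

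**Inputs from the documents.** The classes and the normal heart-rate range of 40–100 bpm are in SAP 18.3.1. The schedule of activities gives ECGs at baseline and at weeks 16 and 24. About 30 participants are planned (SAP 3.2).

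**Assumed inputs.** The documents give no QTcF or heart-rate distribution, so those below are assumptions. The Fridericia relation is QT = QTcF × (60/HR)^(1/3).

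**Step 1: single values with QTcF held constant.**

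- QTcF 430 ms at 50 bpm: 430 × (60/50)^(1/3) = 457 ms, class ]450; 480].
- QTcF 420 ms, 65 to 48 bpm: QT 409 to 452 ms, so normal becomes ]450; 480].
- QTcF 420 ms, 70 to 50 bpm: QT 399 to 446 ms, still normal.

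**Step 2: heart rate below which QT exceeds 450 ms**, from HR = 60 × (QTcF/450)^3.

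| QTcF (ms) | 390 | 400 | 410 | 420 | 430 | 440 | 450 |
|---|---|---|---|---|---|---|---|
| HR (bpm) | 39 | 42 | 45 | 49 | 52 | 56 | 60 |

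The same formula gives the reverse error. QTcF 480 ms has QT of 450 ms or less at about 73 bpm or more, and QTcF 500 ms at about 82 bpm or more.

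**Step 3: size in the actual-value table.** This is a simulation of 1,000,000 participants per setting with no drug effect and two postbaseline ECGs. QTcF has mean 415 ms, between-person SD 15 and within-person SD 8. Heart rate has between-person SD 8 and within-person SD 6 (total √(64 + 36) = 10). An event is baseline at or below 450 ms with at least one postbaseline value above 450 ms.

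| Mean HR (bpm) | QT | QTcF | Difference in 30 participants |
|---|---|---|---|
| 65 | 6.6% | 2.1% | 30 × 0.045 = +1.35 |
| 70 | 3.1% | 2.1% | 30 × 0.010 = +0.3 |
| 75 | 1.2% | 2.1% | 30 × (−0.009) = −0.27 |

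**Step 4: change classes, relevant only if a QT change table is produced.** At QTcF 420 ms, a fall from 75 to 60 bpm moves QT from 389.9 to 420.0 ms, a change of +30.1 ms and so class ]30; 60]. For QTcF 390–430 ms and a starting rate of 65–90 bpm, a fall of about 12 to 20 bpm adds 30 ms. In the simulation, with total heart-rate SD kept near 10, within-person SD from 4.4 to 7 and mean rate 65–75 bpm, a worst-case change above 30 ms occurs in about 5% to 18% of participants for QT, against 0.8% for QTcF.

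**The case against.** The strongest reply is that little in the planned output depends on this, and most of that reply stands.

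- **Change flags.** A reader might take the 5–18% rate as several spurious flags in 30 participants. The documents do not support that, because SAP 18.3 tabulates change abnormalities for QTc only. What remains is the conflict with 18.3.1.
- **Ordinary slowing.** A reader might infer that any everyday fall in heart rate becomes a treatment-emergent abnormality. For the actual-value classes it usually does not: at QTcF 390–440 ms the rate must fall below about 39–56 bpm. The 30 ms change class is crossed more easily, but that is the table 18.3 does not plan for QT.
- **Missed prolongation.** A reader might infer that a prolonged QTcF is lost at faster rates. It is not, because QTcF is classified and shown in its own row.
- **Counts.** The limitation to QTc in the sentence on treatment-emergent numbers most naturally applies to the cumulative counts alone. If it covers both kinds of count, no treatment-emergent QT count is planned. The cross-tabulation and the listing rule would still carry the QT flag.
- **Use of the tables.** SAP 18 plans no between-arm statistical comparison of safety data unless otherwise specified. Heart rate, QTcF and QTcB are reported beside QT, and there is a placebo arm.

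None of this makes the shared cut-offs suitable for an uncorrected interval, and none of it settles which of 18.3 and 18.3.1 governs QT change.

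**Conclusion.** The point holds as a minor one. SAP 18.3.1 classifies uncorrected QT with the limits used for QTcB and QTcF, and 18.3 carries the actual-value result into a cross-tabulation. A QT value can therefore be labelled abnormal through slow heart rate alone, or normal at a faster rate when QTcF is prolonged.

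The numerical effect on that table is small and changes sign: about +1.35, +0.3 and −0.27 participants in 30 at mean heart rates of 65, 70 and 75 bpm. These figures rest on the assumed QTcF and heart-rate distributions, the assumed split of heart-rate variability within and between persons, and the Fridericia relation. The misclassification in the single-value examples needs only the Fridericia relation and the SAP's own limits. No efficacy result and no planned safety test depends on it.

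**What to change.** In SAP 18.3.1, delete QT interval from the lead-in so that the actual-value and change classes apply to QTcF and QTcB only. Keep uncorrected QT in the descriptive summaries and in the listings. In SAP 18.3, say that the interval cross-tabulations, treatment-emergent counts and change tabulations are for QTcF and QTcB, so that the two sections agree.

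The cost is a wording change and one fewer descriptive abnormality table, with no new data. QTcB keeps some rate dependence. If QTcF is constant, QTcB = QTcF × (HR/60)^(1/6), so QTcF 420 ms gives QTcB 407 ms at 50 bpm and 449 ms at 90 bpm. The SAP should therefore name QTcF as the main row.
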